**10.2 Sample Size and Accrual**

POUR occurs in approximately 40% of patients following primary total hip or knee arthroplasty. Risk factors for POUR include male sex, total hip arthroplasty, intrathecal morphine and epidural anesthesia. A sample size of 91 in each arm (tamsulosin versus placebo) is needed with continuity correction if a reduction of 50% (or a POUR incidence of 20%) is to be detected with a power of 80% at a significance level of  $\alpha < 0.05$ . 114 patients are need in each arm assuming an accrual rate of 80% for a total of 228 patients.

**10.3 Data Analyses Plans**

Chi-square test will be used to compare the primary outcome of the incidence of POUR between those taking and those not taking tamsulosin at the time of surgery, as well as the secondary measure of the incidence of discharge to a skilled nursing facility between the two groups. T-test will be used to compare the secondary measures of length of hospital stay and postoperative pain medication requirements (average daily dose) between the two groups. Regression analysis will be performed of other postoperative complications including surgical site infection, deep venous thrombosis, pulmonary embolism, urinary tract infection, pneumonia, cardiovascular event, fevers, and the duration of anesthesia between the two groups. Significance will be set at  $\alpha = 0.05$ .

**11. STUDY MANAGEMENT****11.1 Conflict of Interest**

The investigators of this study have no financial, board or publishing conflicts of interest.

**11.2 Institutional Review Board (IRB) Approval and Consent**

It is expected that the IRB will have the proper representation and function in accordance with federally mandated regulations. The IRB should approve the consent form and protocol.

In obtaining and documenting informed consent, the investigator should comply with the applicable regulatory requirement(s), and should adhere to Good Clinical Practice (GCP) and ethical principles that have their origin in the Declaration of Helsinki.

Before recruitment and enrollment into this study, the patient will be given a full explanation of the study and will be given the opportunity to review the consent form. Each consent form must include all the relevant elements currently required by the FDA, and regional, state, and local regulations. Once this essential information has been provided to the patient, and the investigator is assured that the patient understands the implications of participating in the study, the patient will be asked to give consent to participate in the study by signing an IRB-approved consent form.

Prior to a patient's participation in the trial, the written informed consent form should be signed and personally dated by the patient, and by the person who conducted the informed consent discussion.

### **11.3 Registration Procedures**

All patients must be registered before enrollment to study. Prior to registration, eligibility criteria must be confirmed with the study coordinator.

### **11.4 Data Management and Monitoring/Auditing**

Study coordinator will continually update an anonymized database of patients, their endpoints, secondary measures, adverse events.

### **11.5 Adherence to the Protocol**

Except for an emergency situation in which proper care for the protection, safety, and well-being of the study patient requires alternative treatment, the study shall be conducted exactly as described in the approved protocol.

#### **11.5.1 Emergency Modifications**

Investigators may implement a deviation from, or a change of, the protocol to eliminate an immediate hazard(s) to trial subjects without prior IRB approval.

#### **11.5.2 Other Protocol Deviations/Violations**

All other planned deviations from the protocol must have prior approval by the Principal Investigator and the IRB. According to the IRB, a protocol deviation is any unplanned variance from an IRB approved protocol that:

- is generally noted or recognized after it occurs,
- has no substantive effect on the risks to research participants,
- has no substantive effect on the scientific integrity of the research plan or the value of the data collected, or
- did not result from willful or knowing misconduct on the part of the investigator(s).

An unplanned protocol variance is considered a violation if the variance:

- has harmed or increased the risk of harm to one or more research participants,
- has damaged the scientific integrity of the data collected for the study,
- results from willful or knowing misconduct on the part of the investigator(s), or
- demonstrates serious or continuing noncompliance with federal regulations, state laws, or University policies.

If a deviation or violation occurs without prior approval from the Principal Investigator, please follow the guidelines below:

**Protocol Deviations:** Personnel will report to any data and safety monitoring committee in accordance with their policies. Deviations should be summarized and reported to the IRB at the time of continuing review.

**Protocol Violations:** Study personnel should report violations within one (1) week of the investigator becoming aware of the event using the same IRB online mechanism used to report unanticipated problems.

#### **11.6 Amendments to the Protocol**

Should amendments to the protocol be required, the amendments will be originated and documented by the Principal Investigator. It should also be noted that when an amendment to the protocol substantially alters the study design or the potential risk to the patient, a revised consent form might be required.

The written amendment, and, if required, the amended consent form, must be sent to the IRB for approval prior to implementation.

#### **11.7 Record Retention**

Study documentation includes all Case Report Forms, data correction forms or queries, source documents, monitoring logs/letters, and regulatory documents (e.g., protocol and amendments, IRB correspondence and approval, signed patient consent forms).

Source documents include all recordings of observations or notations of clinical activities and all reports and records necessary for the evaluation and reconstruction of the clinical research study.

Government agency regulations and directives require that the study investigator must retain all study documentation pertaining to the conduct of a clinical trial. Study documents should be kept on file until three years after the completion and final study report of this investigational study.

#### **11.8 Obligations of Investigators**

The Principal Investigator is responsible for the conduct of the clinical trial at the site in accordance with Title 21 of the Code of Federal Regulations and/or the Declaration of Helsinki. The Principal Investigator is responsible for personally overseeing the treatment of all study patients. The Principal Investigator must assure that all study site personnel, including sub-investigators and other study staff members, adhere to the study protocol and all FDA/GCP/NCI regulations and guidelines regarding clinical trials both during and after study completion.

The Principal Investigator will be responsible for assuring that all the required data will be collected and entered onto the Case Report Forms. Periodically, monitoring visits will be conducted and the Principal Investigator will provide access to his/her original records to permit verification of proper entry of data. At the completion of the study, all Case Report Forms will be reviewed by the Principal Investigator and will require his/her final signature to verify the accuracy of the data.

	
Appendix 1: AUA Symptom Index
 
American Urological Association (AUA) Symptom Score

---	---

Patient ID: \_\_\_\_\_ Date: \_\_\_\_\_

**Have you noticed any of the following when you have gone to the bathroom to urinate over the past two weeks?**

Circle the correct answer for you and write your score in the right-hand column.

	Not at all	Less than 1 time in 5	Less than half the time	About half the time	More than half the time	Almost always	Your score
Incomplete emptying – It does not feel like I empty my bladder all the way.	0	1	2	3	4	5	
Frequency – I have to go again less than two hours after I finish urinating.	0	1	2	3	4	5	
Intermittency – I stop and start again several times when I urinate.	0	1	2	3	4	5	
Weak stream – I have a weak urinary stream.	0	1	2	3	4	5	
Straining – I have to push or strain to begin urination.	0	1	2	3	4	5	
	None	1 time	2 times	3 times	4 times	5 times or more	Your score
Nocturia – I get up to urinate after I go to bed until the time I get up in the morning.	0	1	2	3	4	5	

**Total AUA Symptom Score**

 
University of Michigan Health System
	
Appendix 2:  Toxicity Assessment Survey

---	--

Patient ID: \_\_\_\_\_ Date: \_\_\_\_\_  
\_\_\_\_\_

**Are you experiencing any of the following symptoms?**

1. Dizziness: yes / no
2. Headache: yes / no
3. Palpitations (a rapid, fluttering, or pounding heart): yes / no
4. Fainting: yes / no
5. Drowsiness: yes / no

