## **5.2 Procedures During Treatment**

### **5.2.1 Preoperative**

- Physical exam, vital signs (Standard of Care)
- Hematology (Standard of Care)
- Serum chemistries (Standard of Care)
- Completion of the AUA Symptom Index by the patient
- Completion of the Toxicity Assessment Survey by the patient
- Patient to be given seven capsules of 0.4 mg tamsulosin, with one to be taken daily for the five days before surgery, one on the morning of surgery, and one on the day after surgery. Pills should be administered approximately one half hour following the same meal each day.

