### **5.2.2 Postoperative**

- Tamsulosin/placebo taken on postoperative day one
- Completion of the Toxicity Assessment Survey by the patient on post-op day one

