## 7.2 Adverse Event Monitoring

A study coordinator will monitor for AEs with the use of the patient surveys, at the 2-week follow-up appointment, and with a chart review following the 30-day end-of-study-treatment timepoint. Adverse events will be reported in compliance with the IRB standard reporting guidelines. Additionally, certain adverse events must be reported in an expedited manner to allow for optimal monitoring of patient safety and care. See steps 7.4 and 7.5 for requirements for expedited reporting.

All patients experiencing an adverse event, regardless of its relationship to study drug/device, will be monitored until:

- the adverse event resolves or the symptoms or signs that constitute the adverse event return to baseline,
- any abnormal laboratory values have returned to baseline,
- there is a satisfactory explanation other than the study drug for the changes observed, or
- death.

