**10. STATISTICAL CONSIDERATIONS****10.1 Study Design/Study Endpoints**

Prospective, double blinded, randomized single-center study comparing the efficacy of tamsulosin in reducing POUR incidence in primary total hip and knee arthroplasty patients.

Adverse events will be monitored at intervals of 50 (25 in each group). If AEs in the trial group exceed those in the placebo group, and this difference is statistically significant and related to the active drug (tamsulosin), then the study will be terminated. Minor adverse events will be examined via statistical tests (chi-square) at each interval. If there are severe adverse events noted in the intervention group, the study may be halted until further review.

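### The toxicity survey asks only about symptoms at the moment of completion, so no survey question covers the five home dosing days or the morning of surgery

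*Combined protocol and SAP*

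**What the plan says.** Appendix 2 is a five-item yes/no form covering dizziness, headache, palpitations, fainting and drowsiness. Its stem is in the present tense: "Are you experiencing any of the following symptoms". It has no free-text line. The AUA form in Appendix 1 does set a window: "Have you noticed any of the following when you have gone to the bathroom to urinate over the past two weeks".

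The form is scheduled three times:
- Section 5.2.1, preoperative: "Completion of the Toxicity Assessment Survey by the patient". No day is given. The same list contains the hand-out: "Patient to be given seven capsules of 0.4 mg tamsulosin, with one to be taken daily for the five days before surgery".
- Section 5.2.2: "Completion of the Toxicity Assessment Survey by the patient on post-op day one".
- Section 5.3: at follow-up, which the Time and Events Table (5.4) places at two weeks.

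Section 4.1 has the preoperative capsules taken as an outpatient, and allows supply at the preoperative appointment or by mail.

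Section 4.2 names this survey as the instrument for evaluating toxicity. Section 7.2 is broader: "A study coordinator will monitor for AEs with the use of the patient surveys, at the 2-week follow-up appointment", followed by a chart review after the 30-day point. On use of the data, section 10.1 says "Minor adverse events will be examined via statistical tests (chi-square) at each interval", the interval being every 50 patients (25 per group). The Stopping Rules also compare the adverse event rate with the expected rate listed in the protocol.

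**The concern.** The home days are the part of the dosing period in which a symptom is easiest to attribute to the capsule, because there has been no operation yet. A man who was dizzy on the third home day and is well on post-op day one can truthfully answer no on every form. The one on-treatment survey falls on the day after surgery. I take it as a clinical assumption, not stated in the protocol, that anaesthesia and opioids can cause dizziness and drowsiness then, whichever capsule was taken.

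If tamsulosin causes short-lived minor symptoms at home, the survey misses them, while it records post-surgical symptoms common to both arms. Both effects make a difference between arms harder to see in the interim chi-square test. For the rule based on the expected rate, the direction is less clear: missed home symptoms lower the count and post-surgical symptoms raise it. Either way, a present-tense answer is hard to set against the rates in section 7.1.4.

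**Working it through.** No figure in the plan depends on this point, so the check is a count of dosing days and items.

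**Dosing days covered.** Inputs: capsule schedule from 4.1.1 and 5.2.1; survey schedule from 5.2.1, 5.2.2, 5.3 and 5.4.

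| Period | Capsules | Survey question about that period |
|---|---|---|
| Five days before surgery, at home | 5 | None scheduled after hand-out |
| Morning of surgery | 1 | None |
| Post-op day one | 1 | Yes, symptoms at that moment |
| Two-week follow-up | 0 | Symptoms at that moment only |

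Dosing days asked about: 1 of 5 + 1 + 1 = 7, or 14%. The two-week form comes about 14 − 1 = 13 days after the last planned capsule and does not look back.

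**Sensitivity to the unstated preoperative day.** The table treats the preoperative form as a baseline. Two features support this: it is listed with the capsule hand-out in 5.2.1, and in 5.4 the preoperative toxicity evaluation shares a column with informed consent. Against it, section 5.2 is headed as procedures during treatment and gives no day. If the form were completed on a home dosing day or on the morning of surgery, coverage would be at most 2 of 7 (29%), still as a snapshot, and no survey baseline would remain. At least five dosing days go unasked on either reading.

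**Items, as a side check.** Section 7.1.4 lists ten effects associated with alpha-blockers. Matching fainting to syncope and drowsiness to somnolence, the form covers five.
- Drug-related reports, covered: 30 + 7 + 7 + 0 + 2 = 46.
- Drug-related reports, not covered (abnormal ejaculation, asthenia, rhinitis, postural hypotension, dry mouth): 22 + 10 + 3 + 14 + 6 = 55.
- Share not covered: 55 / (46 + 55) = 54%.

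These are reports, and one patient may contribute several. Postural hypotension is 2.9% overall and 2.7% drug related in that table. At 114 per arm this gives 114 × 0.027 = 3.1 to 114 × 0.029 = 3.3 patients. That is an order of magnitude only, because the rates come from a cited long-term study and the course here is seven capsules.

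**The case against.** The strongest reply is that the survey is not the only route. Section 7.2 adds the two-week appointment and a chart review, and 5.4 schedules a history and examination at two weeks. Section 7.3.1 defines adverse events broadly. Section 4.4 ends therapy for an adverse reaction, and 4.6 requires the reason and date of removal on the Case Report Form, so a home event that stops dosing should be recorded. This stands, and it limits the point to symptoms that are not serious and do not stop dosing. What it does not supply is any structured question about the home days at the visit or in the chart review.

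A reader might infer more than the documents support, in four ways:
- *That the safety rules as a whole are weakened.* The rule on more than two serious adverse events, and the provision in 10.1 for severe events, are not stated to depend on this form.
- *That the preoperative form is certainly a baseline.* That is likely, but it is an inference.
- *That postural hypotension goes unmeasured.* It is not a named item, but the dizziness and fainting items cover its symptoms in part, and a yes/no form could not record the blood pressure finding itself.
- *That a definite loss of power follows.* The table in 7.1.4 has no placebo column, and nothing says how long symptoms last, so any power figure would rest on assumed rates and an assumed persistence.

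**Conclusion.** The gap is real and limited. Followed as written, the plan asks patients by survey about one dosing day in seven (at most two if the preoperative form falls within the dosing period), and the day it does ask about is the one after surgery. Minor drug-related symptoms at home can be missed, which bears on the interim chi-square comparison and on the adverse-event-rate part of the Stopping Rules.

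The conclusion assumes that the stem is read literally and that staff do not ask about the home days unprompted. How many events would be lost cannot be derived from the documents. The sample size is not affected. The change is worth making because it is cheap and cannot be made good afterwards: a symptom not asked about near the time is unlikely to be recovered.

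**What to change.** - Day-one form: change the stem to *Since you took your first study capsule, have you had...*, with a before-surgery / after-surgery tick box for each item.
- Two-week form: change the stem to *Since the last survey, have you had...*.
- Section 5.2.1: state that the preoperative form is completed before the first capsule, including when capsules are mailed.
- Optional: add an item on light-headedness on standing, since orthostatic or postural hypotension is listed in 1.2, 7.1.4 and 8.1 and the present items cover it only in part.

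The cost is one reworded form and an IRB submission, with no new visit and no change to enrolment. The downside is about one week of recall on the day-one form and two weeks on the second, and higher adverse event counts in both arms. Recall error should fall alike on both arms while the blind holds. Because counts will rise, the comparison with the expected rate should state which events and which period are counted. If enrolment has begun, record which form each patient completed.

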**Patient Prescription Pain Medication Log**

Once you are discharged, you will be instructed to take a **prescription** pain medication according to your surgeon's orders and pain levels. We would like to know how you are controlling your pain post-surgery from the day of your discharge up until your first follow up appointment. If you would please note how many pills of the **prescription medication** you take and how many times per day, it would be greatly appreciated. Then please bring this chart with you to your appointment and the research coordinator can get it from you. Thank you for your time and willingness to participate in our research. It is greatly appreciated.

Wishes for a speedy recovery,  
The University of Michigan Orthopaedic Surgery Research Team

Patient ID Number \_\_\_\_\_

Prescription Medication Name: \_\_\_\_\_

\_\_\_\_\_ Dosage: \_\_\_\_\_ (mg)

	Pills taken					
EXAMPLE	1	0	2	0	1	1
Day 1						
Day 2						
Day 3						
Day 4						
Day 5						
Day 6						
Day 7						
Day 8						
Day 9						
Day 10						
Day 11						
Day 12						
Day 13						
Day 14						
Day 15						
Day 16						
Day 17						
Day 18						

Principal Investigator (PI) Oversight Meeting Log

PI:  
Study:  
Sponsor:

Instructions: This log documents meetings held with the PI to review study status, enrollments, AEs, MAIs, lab results and issues/deviations.

Date of Discussion	Patient# (if applicable)	Topics Discussed	Names of Attendees	P D
